12. CLINICAL PHARMACOKINETIC AND PHARMACODYNAMIC ANALYSES

Not applicable.

13. OTHER ANALYSES

No other analyses are planned for this study.

14. INTERIM ANALYSIS

After no fewer than 50 subjects have completed 6 months of study treatment and approximately 20 subjects have completed 12 months of study treatment, the database will be archived and all available safety and efficacy data will be analyzed for regulatory reporting reasons. Additional analyses will be performed as required for regulatory purposes, such as subsequent safety updates if required and development of the final clinical study report.

Due to the early termination of the study, the interim analysis above will not be performed. All collected data will be included in the final analyses and reported.

15. DATA MONITORING/REVIEW COMMITTEE

A data monitoring committee (DMC) will be involved in the management of this study. The purpose of the DMC is to monitor safety and tolerability of the investigational product and to protect the interests of subjects in the study and of those still to be entered. The data provided to the DMC will not be considered 'clean' until the database is locked.

The analyses for DMC will be a subset of the analyses specified in this SAP. Further details regarding the DMC can be found in the DMC charter, which will be available before the administration of investigational product.

16. COMPUTER METHODS

Statistical analyses will be performed using Version 9.3 (or newer) of SAS[®] on a suitably qualified environment.

17. CHANGES TO ANALYSES SPECIFIED IN PROTOCOL

Not applicable.

18. DATA HANDLING CONVENTIONS

18.1 General Data Reporting Conventions

Continuous variables will be summarized using the following descriptive statistics: n, mean, median, SD, minimum, and maximum. Unless specified otherwise, summary statistics will be presented to 1 more significant digit than the raw data. The minimum and maximum values will be presented to the same number of decimal places as the raw data; the mean and median will be presented to 1 more decimal place than the raw data; and the SD and standard error will be presented to 2 more decimal places than the raw data.

Categorical and count variables will be summarized by the number of subjects (n) and the percent of subjects in each category. Percentages will be presented to 1 decimal place.

P-values will generally be presented to 4 decimal places; values less than 0.001 will be presented as <0.001.

18.2 Derived Efficacy Endpoints

The ADHD-RS-5 Child, Home Version total score will be calculated as the sum of the individual items from the ADHD-RS-5 Child, Home Version. The ADHD-RS/ADHD-RS-5 Child, Home Version consists of 18 items designed to reflect current symptomatology of ADHD based on Diagnostic and Statistical Manual of Mental Disorders Five Edition (DSM-5.) criteria. Each item is scored on a 4-point scale ranging from 0 (reflecting no symptoms) to 3 (reflecting severe symptoms) with total scores ranging from 0-54. As noted in Section 10.2, the items in the ADHD-RS-5 Child, Home Version will also be grouped into 2 subscales: hyperactivity/impulsivity (9 items for hyperactivity/impulsivity) and inattentiveness (9 items for inattentiveness), with subscale scores ranging from 0-27.

A missing individual item in the ADHD-RS-5 Child, Home Version is imputed as follows (DuPaul et al.1998): if only 1 single item is missing in a given subscale, the mean score for all other items in the subscale for the specific visit is imputed as the score rounded up to the nearest integer for the missing score. The total score is computed as the sum of the imputed subscale scores. If more than 1 item is missing in a subscale then the subscale score and total score would be missing.

18.3 Association of Early Termination Assessments to Scheduled Visits

For purposes of reporting early termination assessments during the study, each early termination visit will be assigned the next nominal visit number after the last completed visit. This rule applies to both efficacy variables (e g , ADHD-RS-5 - Child, Home Version total score) and safety variables (e g , vital signs) except for the lab data, which will be analyzed and/or summarized by visit.

18.4 Repeated or Unscheduled Assessments of Safety Parameters

If a subject has repeated assessments before the start of investigational product, then the results from the final assessment made prior to the start of investigational product will be used as baseline.

If a subject has repeated assessments at any post-baseline visit, the first recorded assessment will be assigned to the visit for generating descriptive statistics. For vital signs (sitting systolic and diastolic blood pressure, and pulse), this will be the average of the 3 measurements from the first recorded assessment.

If final on-treatment safety assessments are repeated or unscheduled, the last post-baseline assessment will be used as the final on-treatment assessment for generating descriptive statistics. For vital signs (sitting systolic and diastolic blood pressure, and pulse), this will be the average of the 3 measurements from the last post-baseline assessment.

However, all post-baseline assessments will be used for PCI value determination and all assessments will be presented in the data listings.

All repeat and unscheduled visits will be listed.

18.5 Missing Dispensed or Returned Date or Number of Capsules of Investigational Product

When the date of the last dose of investigational product is missing for a subject in the Safety Set, all efforts should be made to obtain the date from the investigator. If it is still missing after all efforts, then the last visit date when investigational product was returned will be used in the calculation of investigational product exposure.

18.6 Missing Date Information for Prior or Concomitant Medications

For prior or concomitant medications, incomplete (i.e., partially missing) start date and/or stop date will be imputed. When the start date and the stop date are both incomplete for a subject, impute the start date first.

18.6.1 Incomplete Start Date

The following rules will be applied to impute the missing numerical fields. If the stop date is complete and the imputed start date is after the stop date, then the start date will be imputed using the stop date.

Missing day and month

- If the year of the incomplete start date is the same as the year of the date of the first dose of investigational product, then the day and month of the date of the first dose of investigational product will be assigned to the missing fields
- If the year of the incomplete start date is before the year of the date of the first dose of investigational product, then 31 December will be assigned to the missing fields

- If the year of the incomplete start date is after the year of the date of the first dose of investigational product, then 01 January will be assigned to the missing fields.

Missing month only

- The day will be treated as missing and both month and day will be replaced according to the above procedure.

Missing day only

- If the month and year of the incomplete start date are the same as the month and year of the date of the first dose of investigational product, then the day of the date of the first dose of investigational product will be assigned to the missing day
- If either the year is before the year of the date of the first dose of investigational product or if both years are the same but the month is before the month of the date of the first dose of investigational product, then the last day of the month will be assigned to the missing day
- If either the year is after the year of the date of the first dose of investigational product or if both years are the same but the month is after the month of the date of the first dose of investigational product, then the first day of the month will be assigned to the missing day.

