9. PRIOR AND CONCOMITANT MEDICATION

Version WHODRUG March 2017 of the WHO drug dictionary will be used to classify prior and concomitant medications by preferred term.

Prior medication is defined as any medication taken prior to the date of first dose of investigational product in this study.

Concomitant medication is defined as any medication with a start date prior to the date of the first dose of investigational product and continuing after the first dose of investigational product or with a start date between the dates of the first dose and last dose of investigational product, inclusive.

Any medication with a start date after the date of the last dose of investigational product (post-treatment) will not be considered a concomitant medication

Both prior and concomitant medication usage will be summarized separately by the number and percentage of subjects receiving each medication within each preferred term by treatment group of the antecedent studies, current treatment (SHP465) for each enrollment type, and overall for the Safety Set. Medications can be counted both as prior and concomitant medication. Multiple medication usage by a subject in the same category will be counted only once for the purpose of the summaries.

All prior, concomitant and post-treatment medications will be listed for the Safety Set.

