18.6.2 Incomplete Stop Date

The following rules will be applied to impute the missing numerical fields. If the date of the last dose of investigational product is missing, then replace it with the last visit date. If the imputed stop date is before the start date (imputed or non-imputed start date), then the imputed stop date will be equal to the start date.

Missing day and month

- If the year of the incomplete stop date is the same as the year as of the date of the last dose of investigational product, then the day and month of the date of the last dose of investigational product will be assigned to the missing fields
- If the year of the incomplete stop date is before the year of the date of the last dose of investigational product, then 31 December will be assigned to the missing fields
- If the year of the incomplete stop date is after the year of the date of the last dose of investigational product, then 01 January will be assigned to the missing fields.

Missing month only

- The day will be treated as missing and both month and day will be replaced according to the above procedure.

Missing day only

- If the month and year of the incomplete stop date are the same as the month and year of the date of the last dose of investigational product, then the day of the date of the last dose of investigational product will be assigned to the missing day

- If either the year is before the year of the date of the last dose of investigational product or if both years are the same but the month is before the month of the date of the last dose of investigational product, then the last day of the month will be assigned to the missing day
- If either the year is after the year of the last dose of investigational product or if both years are the same but the month is after the month of the date of the last dose of investigational product, then the first day of the month will be assigned to the missing day.

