18.7 Missing Date Information for Adverse Events

For AEs, incomplete (i.e., partially missing) start dates will be imputed and will follow the same rules as in Section 18.6.1. Incomplete stop dates will not be imputed.

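### SAP 18.6.1 ignores a known stop month when the stop day is missing, so a medication that ended before dosing can be counted as concomitant if its start is year-only and in the first-dose year

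*SAP*

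**What the plan says.** - **Order (SAP 18.6).** "When the start date and the stop date are both incomplete for a subject, impute the start date first".
- **Start with month and day missing, in the first-dose year (SAP 18.6.1).** "then the day and month of the date of the first dose of investigational product will be assigned to the missing fields". A year-only start in an earlier year goes to 31 December of that year.
- **Start with only the day missing, in a month before first dose (SAP 18.6.1).** "then the last day of the month will be assigned to the missing day".
- **Check on the imputed start (SAP 18.6.1).** The start is pulled back to the stop date only "If the stop date is complete and the imputed start date is after the stop date".
- **Check on the imputed stop (SAP 18.6.2).** If the imputed stop falls before the start, whether or not that start was itself imputed, "then the imputed stop date will be equal to the start date".
- **Adverse events (SAP 18.7).** Partial start dates follow 18.6.1. For stop dates: "Incomplete stop dates will not be imputed".
- **Use of the dates.** SAP 9: "Prior medication is defined as any medication taken prior to the date of first dose of investigational product in this study". A start from the first to the last dose date, inclusive, makes a medication concomitant. SAP 11.1 makes an event with a start on or after first dose treatment-emergent.

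**The concern.** Moving an unknown start to the first-dose date is a common cautious convention, and it is reasonable while the record leaves open whether exposure overlapped treatment. Here the record does not leave it open: a stop month before the first-dose month rules out any use on or after first dose. The SAP accepts this reasoning when the stop date is complete, because the check then pulls the start back. When only the stop day is missing, the same information is ignored, and the 18.6.2 reset overwrites the recorded stop month to agree with an imputed start.

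The stake is the classification of the record. A medication that ended before dosing appears in the concomitant summary and disappears from the prior summary. SAP 9 lets a medication count in both tables, so a purely cautious rule would have kept it in the prior table.

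**Working it through.** The plan states no figure to reproduce. The check applies the rules literally to example dates. First dose 15 Jun 2018 and last dose 10 Dec 2018 are assumptions.

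**1. Medication, start 2018 (no month), stop Mar 2018 (no day).**
- Start: year equals first-dose year, so 15 Jun 2018.
- Check in 18.6.1: not run, because the stop is incomplete.
- Stop: the month is before the last-dose month, so 31 Mar 2018.
- Check in 18.6.2: 31 Mar is before 15 Jun, so the stop becomes 15 Jun 2018.
- SAP 9: the start is not before first dose, so not prior; the start is on the first-dose date, so concomitant.

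**2. Same start, complete stop 20 Mar 2018.** The check runs and the start becomes 20 Mar 2018. The medication is prior only, which is correct.

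**3. Adverse event with the dates of step 1.** The start becomes 15 Jun 2018 and the stop month is never compared with it, so the event is a TEAE. With the complete stop of step 2 it is not.

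**4. Enumeration.** Take every month-level start and stop pair from January 2016 on, with the start not after the stop and the stop month before June 2018.
- Start in 2018: five possible start months, so 5 + 4 + 3 + 2 + 1 = 15 pairs.
- Start in 2016 or 2017: 24 start months and 29 possible stop months, so the sum of (30 − s) for s = 1 to 24 is 720 − 300 = 420 pairs.

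| Start missing | Stop | Start in first-dose year | Start in earlier year |
|---|---|---|---|
| day only | complete | 0/15 concomitant | 0/420 |
| day only | day missing | 0/15 | 0/420 |
| month and day | complete | 0/15 | 0/420 |
| month and day | day missing | **15/15** | 0/420 |

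None of these records should be concomitant. The failure is confined to one cell and is certain within it.

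**5. Start capped at the latest date a partial stop allows.** In step 1 that date is 31 Mar 2018. Start and stop both become 31 Mar 2018, and the medication is prior only. With the cap, no enumerated record is concomitant. The event in step 3 starts before first dose and is not a TEAE.

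**6. Should the 18.6.2 reset also be limited to starts that were not imputed?** Assume last dose 28 Apr 2018, an earlier first dose, start May 2018 and stop 2018. The start becomes 1 May 2018. The stop has the last-dose year, so it becomes 28 Apr 2018. The cap is 31 Dec 2018 and does not act. The present reset gives a stop of 1 May; the limited reset would leave the stop before the start.

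**The case against.** The strongest reply is that this hardly matters, and much of that stands.

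- **The trigger is narrow.** A reader might infer that partial start dates in general are pushed onto Day 1. They are not: day-only gaps, starts in earlier years and records with complete stop dates all come out right. Long-standing items in a lifetime medication history (Protocol 7.1.1.1) tend to start in earlier years.
- **Washed-out drugs are a weak example.** A reader might infer that stimulants or sedatives stopped for washout will be reported as taken on study. Washout is directed by the site after consent and counted in days before Visit 2 (Protocol 5.2.2, Table 3; 7.1.1.2), so the stop day will often be known and the check will then run. ADHD medication history is also summarized separately under SAP 7.2 without a prior/concomitant split, so a misdated stimulant would still appear there.
- **No vital-sign or sleep result changes.** A reader might infer confounding of blood pressure, pulse or sleep findings. No analysis in SAP 10 or 11 adjusts for, censors at or excludes on concomitant medication.
- **The adverse-event route is nearly empty.** Events are collected only from consent (Protocol 7.2.3.3, 8.1). Group B screening is planned at up to 32 days (Protocol 3.2), and Group A consents at Visit 2 with dosing the next morning (Protocol 7.1.1.3). An event after a dated consent with an unknown start month but a known stop month is implausible.

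These points limit how often the error occurs and what it touches. They do not make the classification right when it does occur, and no other section of the SAP overrides the rule.

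**Conclusion.** The rule is wrong as written for one date pattern: a start with no month in the first-dose year, and a stop with no day in a known month of that year before the first-dose month. Every such medication is counted as concomitant and lost from the prior table. The same pattern in an adverse event would create a TEAE, but should be rare. The damage is confined to descriptive counts in a study with no formal tests, so this is a minor correction.

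The number of affected records cannot be found from the documents. Simulation can only describe records that already have a year-only start and a month-and-year stop before the first-dose month. Among those, with first dose assumed uniform from October 2017 to November 2018, about 66% are misclassified if courses last 30–180 days and end 7–60 days before dosing. The figure is about 44% for courses of 30–365 days ending 7–30 days before, and about 32% for 30–365 days ending 30–120 days before. These figures mainly reflect how often the assumed course began in the first-dose year. Reading them as an error rate for the medication tables would not be supported.

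**What to change.** In SAP 18.6.1, replace the present check with:

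> If the imputed start date is later than the stop date, or later than the latest date consistent with a partial stop date (last day of the known month, or 31 December of the known year), the start date is set to that date.

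In SAP 18.7, state that a partial adverse-event stop date is used for this check only and is otherwise still not imputed.

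Leave the reset in SAP 18.6.2 unchanged, for the reason shown in the last step of the working.

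The cost is one revised sentence, one added sentence and a small edit to the date program. No new data are needed. Listing the records with this pattern before database lock would show whether any table changes.

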18.6.2 Incomplete Stop Date

The following rules will be applied to impute the missing numerical fields. If the date of the last dose of investigational product is missing, then replace it with the last visit date. If the imputed stop date is before the start date (imputed or non-imputed start date), then the imputed stop date will be equal to the start date.

Missing day and month

- If the year of the incomplete stop date is the same as the year as of the date of the last dose of investigational product, then the day and month of the date of the last dose of investigational product will be assigned to the missing fields
- If the year of the incomplete stop date is before the year of the date of the last dose of investigational product, then 31 December will be assigned to the missing fields
- If the year of the incomplete stop date is after the year of the date of the last dose of investigational product, then 01 January will be assigned to the missing fields.

Missing month only

- The day will be treated as missing and both month and day will be replaced according to the above procedure.

Missing day only

- If the month and year of the incomplete stop date are the same as the month and year of the date of the last dose of investigational product, then the day of the date of the last dose of investigational product will be assigned to the missing day

- If either the year is before the year of the date of the last dose of investigational product or if both years are the same but the month is before the month of the date of the last dose of investigational product, then the last day of the month will be assigned to the missing day
- If either the year is after the year of the last dose of investigational product or if both years are the same but the month is after the month of the date of the last dose of investigational product, then the first day of the month will be assigned to the missing day.

18.7 Missing Date Information for Adverse Events

For AEs, incomplete (i.e., partially missing) start dates will be imputed and will follow the same rules as in Section 18.6.1. Incomplete stop dates will not be imputed.

18.8 Missing Severity Assessment for Adverse Events

If severity is missing for an AE starting prior to the date of the first dose of investigational product, then a severity of “Mild” will be assigned. If the severity is missing for an AE starting on or after the date of the first dose of investigational product, then a severity of “Severe” will be assigned. The imputed values for severity assessment will be used for incidence summaries, while the actual values will be used in data listings.

18.9 Missing Relationship to Investigational Product for Adverse Events

If the relationship to investigational product is missing for an AE starting on or after the date of the first dose of investigational product, a causality of “Related” will be assigned. The imputed values for relationship to investigational product will be used for incidence summaries, while the actual values will be presented in data listings.

18.10 Character Values of Clinical Laboratory Variables

The actual values of clinical laboratory variables as reported in the database will be presented in data listings. No coded values (e.g., when a character string is reported for a numerical variable) are necessary.

20. TABLE OF CONTENTS FOR FIGURES, TABLES, AND LISTINGS

Table of contents for figures, tables and listings will be provided in a separate document with the table, figure and listing templates.
